## **9.3 Treatments**

### **Study treatment**

Descriptive statistics will be provided for exposure to study treatment using the Safety Set, PTF and STR subgroups. The number of ranibizumab injections will be presented by visit and cumulatively. Summaries will be presented for the injections in the study eye and the fellow treated eye as appropriate. Other data related to the application procedure will be summarized as appropriate.

The proportion of patients who received bilateral injections of ranibizumab (both the study eye and fellow eye injected at the same visit) will be summarized by visit.

Analyses of the treatment exposure will include:

- Treatment frequency (total number of injections and number of injections by visit)
- Reason for PRN treatment (patient symptoms, BCVA decline, or OCT criteria)
- Compliance to treatment regimen (if treatment given monthly per protocol or as a response to changes in patient symptoms, BCVA or OCT)

Reasons for discontinuation from the study will be summarized.

### **Concomitant therapies**

The number and percentage of patients taking concomitant therapies will be summarized by preferred term according to the WHO Drug Reference List dictionary using the Safety Set. Summaries will be presented over two time periods: therapies received prior to the start of study treatment and therapies received after the start of study treatment.

## **9.4 Analysis of the primary variable(s)**

The primary objective is to demonstrate that the mean change from baseline in CSRT (as determined by OCT) at Day 90 is less than zero.

### **9.4.1 Variable(s)**

The primary variable will be the difference from baseline to Day 90 in CSRT.

### **9.4.3 Handling of missing values/censoring/discontinuations**

In the event that CSRT is missing for Day 90, the analysis will follow an LOCF (Last Observation Carried Forward) approach for the Full Analysis Set. This will only be done for the primary outcome.

#### **9.4.4 Supportive analyses**

For sensitivity purposes, the primary analysis will be repeated using the PPS. Any major discrepancies in the results across analyses will be investigated as necessary. For the PPS, it is assumed that a complete set of valid observations for the efficacy endpoints will be available. Therefore, no general rules for handling of missing values are specified. In case missing values occur, details regarding their handling will be described in a Statistical Analysis Plan.

### **9.5 Analysis of secondary variables**

#### **9.5.1 Efficacy variable**

**Secondary variables are:**

[figure not shown]
**From Optical Coherence Tomography (OCT):**

[figure not shown]
- Mean change from baseline to visits up to Day 180 in Subfoveal Retinal Thickness (SRT), Central Subfield Retinal Thickness (CSRT), and Central Subfield Retinal Volume (CSRV).
- Presence or absence of qualitative OCT parameters (intra-retinal cystoid changes (IRCs), subretinal fluid (SF), pigment epithelial detachments (PEDs), or dry retina).
- Mean change from baseline to visits up to Day 180 in PED height, SF volume, and IRC volume.

**From visual acuity:**

- Mean change in best corrected visual acuity (BCVA) from Baseline to visits up to Day 180.
- Mean change in BCVA from Day 90 to Day 180.
- Proportions of patients gaining  $\geq 5$ ,  $\geq 10$  and  $\geq 15$  ETDRS letters from Baseline at visits up to Day 180.
- Proportion maintaining vision ( $< 15$  ETDRS letters lost from baseline) at visits up to Day 180.

The analysis of the secondary efficacy objectives will focus on the FAS. At all time-points assessed, each efficacy variable will be presented graphically and descriptive statistics provided based on absolute values and changes from baseline.

## **9.5.2 Safety variables**

Safety parameters will include adverse events, the results of ophthalmic examinations, intraocular pressure (IOP), vital signs, and laboratory results if reported as AE.

All safety analyses will be performed using the Safety Set.

### **Adverse Events**

Adverse events will be deemed treatment emergent if the onset date is on or after the date of first study treatment. Any adverse events recorded prior to the start of study treatment will be listed as prior medical conditions. Only treatment-emergent adverse events will be summarized.

Adverse events will be summarized by presenting the number and percentage of patients having any adverse event, having an eye-related adverse event, having an adverse event in each primary system organ class and having each individual adverse event based on the preferred term. Patients who experienced multiple adverse events for a preferred term will be counted once, similarly for patients with multiple adverse events per system organ class.

All the ocular AEs after the first treatment of the fellow eye will be listed according to whether they occurred in the study eye or fellow treated eye.

All other information collected (e.g., severity or relationship to study treatment) will be tabulated and listed as appropriate. Summary tables will also be presented for the subset of adverse events suspected to be treatment related.

Deaths, serious adverse events, and adverse events leading to discontinuation of study treatment will be listed separately and, if appropriate, summarized by primary system organ class and preferred term.

[figure not shown]
### **Vital signs and special tests**

Vital signs will be summarized by presenting shift tables using clinically notable abnormal ranges with thresholds representing clinical relevant abnormality and by presenting descriptive statistics of raw data and change from Baseline. Values outside the clinically notable range will be listed by patient and treatment group and flagged in data listings. IOP measurements will be presented descriptively (absolute values and change from baseline).

## **9.6 Interim analyses**

An interim analysis will be conducted after the first 50 patients have completed visits up to Day 90. This will be used primarily to provide preliminary data on the safety of ranibizumab in patients with nAMD with either primary treatment failure or suboptimal treatment response to aflibercept. Descriptive analyses will be carried out on the main safety and efficacy variables. The results from this Day 90 analysis will be submitted for publication. As no hypothesis tests will be carried out, no statistical adjustments are required.

## **10 Ethical considerations**

### **10.1 Regulatory and ethical compliance**

[figure not shown]
This clinical study was designed and shall be implemented and reported in accordance with the ICH Harmonized Tripartite Guidelines for Good Clinical Practice, with applicable local regulations (including European Directive 2001/20/EC, US CFR 21, and Japanese Ministry of Health, Labor, and Welfare), and with the ethical principles laid down in the Declaration of Helsinki.

### **10.2 Informed consent procedures**

Eligible patients may only be included in the study after providing written (witnessed, where required by law or regulation), IEC-approved informed consent, or, if incapable of doing so, after such consent has been provided by a legally acceptable representative(s) of the patient. In cases where the patient's representative gives consent, the patient should be informed about the study to the extent possible given his/her understanding. If the patient is capable of doing so, he/she should indicate assent by personally signing and dating the written informed consent document or a separate assent form. Informed consent must be obtained before conducting any study-specific procedures (i.e. all of the procedures described in the protocol). The process of obtaining informed consent should be documented in the patient source documents.

Novartis will provide to Investigators in a separate document a proposed informed consent form that complies with the ICH GCP guideline and regulatory requirements and is considered appropriate for this study. Any changes to the proposed consent form suggested by the Investigator must be agreed to by Novartis before submission to the IEC, and a copy of the approved version must be provided to the Novartis monitor after IEC approval.

Women of child bearing potential should be informed that taking the study drug may involve unknown risks to the fetus if pregnancy were to occur during the study and agree that in order to participate in the study they must adhere to the contraception requirement for the duration of the study. If there is any question that the patient will not reliably comply, they should not be entered in the study.

In the event that Novartis wants to perform testing on the samples that are not described in this protocol, additional IEC approval will be obtained.

### **10.3 Responsibilities of the Investigator and the IEC**

Before initiating a trial, the Investigator/institution should obtain approval/favorable opinion Independent Ethics Committee (IEC) for the trial protocol, written informed consent form, consent form updates, subject recruitment procedures (e.g., advertisements) and any other written information to be provided to patients. Prior to study start, the Investigator is required to sign a protocol signature page confirming his/her agreement to conduct the study in accordance with these documents and all of the instructions and procedures found in this protocol and to give access to all relevant data and records to Novartis monitors, auditors, Novartis Quality Assurance representatives, designated agents of Novartis, IECs, and regulatory authorities as required. If an inspection of the clinical site is requested by a regulatory authority, the Investigator must inform Novartis immediately that this request has been made.

### **10.4 Publication of study protocol and results**

Novartis assures that the key design elements of this protocol will be posted in a publicly accessible database such as [clinicaltrials.gov](http://clinicaltrials.gov). Efficacy and safety data will be presented at both national and international scientific meetings. In addition, upon study completion and finalization of the study report the results of this trial will be submitted for publication and posted in a publicly accessible database of clinical trial results. Future authorship will be determined according to published ICMJE criteria (<http://www.icmje.org/>).

## **11 Protocol adherence**

Investigators ascertain they will apply due diligence to avoid protocol deviations. Under no circumstances should the Investigator contact Novartis or its agents, if any, monitoring the trial to request approval of a protocol deviation, as requests to approve deviations will not be granted.

This protocol defines the study objectives, the study procedures and the data to be collected on study participants. Additional assessments required to ensure safety of patients should be administered as deemed necessary on a case by case basis. Under no circumstances should an Investigator collect additional data or conduct any additional procedures for any research related purpose involving any investigational drugs.

Investigators ascertain they will apply due diligence to avoid protocol deviations. If an Investigator feels a protocol deviation would improve the conduct of the study this must be considered a protocol amendment, and unless such an amendment is agreed upon by Novartis and approved by the IRB/IEC and health authorities, where required, it cannot be implemented. All significant protocol deviations will be recorded and reported in the clinical study report.

### **11.1 Protocol Amendments**

Any change or addition to the protocol can only be made in a written protocol amendment that must be approved by Novartis, Health Authorities where required, and the IEC prior to implementation. Only amendments that are intended to eliminate an apparent immediate hazard to patients may be implemented immediately provided the Health Authorities are subsequently notified by protocol amendment and the reviewing IEC is notified.

Notwithstanding the need for approval of formal protocol amendments, the Investigator is expected to take any immediate action required for the safety of any patient included in this study, even if this action represents a deviation from the protocol. In such cases, the reporting requirements identified in section 7 Safety Monitoring should be followed.

## **13 Appendix 1: Clinically notable laboratory values and vital signs**

The criteria for clinically notable abnormal vital signs are shown in. In order to be identified as being potentially clinically notable abnormal, an on-treatment vital sign value would need to meet the criterion value, and represent a change of at least the magnitude noted in the critical values column.

**Table 13-1 Clinically notable abnormal vital signs**

Variable	Type of abnormality	Critical value
Pulse rate (bpm)	High	Either >120 with an increase from baseline>25 or >130 absolute
	Low	Either <50 with a decrease from baseline>30 or <40 absolute
Systolic blood pressure (mmHg)	High	Either >180 with an increase from baseline>30 or >200 absolute
	Low	Either<90 with a decrease from baseline>30 or <75 absolute
Diastolic blood pressure (mmHg)	High	Either >105 with an increase from baseline>20 or >115 absolute
	Low	Either <50 with a decrease from baseline>20 or <40 absolute

Data will be analyzed by [REDACTED] according to the data analysis section 9 of the study protocol which is available in Appendix 16.1.1 of the clinical study report (CSR). Important information is given in the following sections and details are provided, as applicable, in Appendix 16.1.9 of the CSR.

Following are the changes from the protocol planned analysis:

- [REDACTED]
- SF volume and IRC volume were mentioned in the protocol as secondary efficacy variables. Due to technical limitations, there is no robust way in the reading center to assess these two parameters. CSRT thickness and subfoveal retinal thickness will be used to assess SF volume, and maximum height of intra-retinal cysts (IRC) will be used to assess IRC volume.
- ‘Intra-retinal cystoid changes’ was listed as a variable in the secondary objectives section. This is being assessed by presence of intraretinal fluid and whether some of the intraretinal fluid is of cystoid origin.
- [REDACTED]

This is a phase IV, unmasked, uncontrolled, single arm, and multicenter study in patients diagnosed with visual impairment due to nAMD who have been treated with aflibercept and where either no treatment response has been achieved or where there is suboptimal treatment response. The study will enroll 150 patients in 30 ophthalmology centers in Western European countries. Patients will be enrolled according to 2 subgroups: primary treatment failure subgroup (maximum of 30 patients) or suboptimal response subgroup.

The study includes 8 study visits over a minimum of 6 months. All patients with nAMD and eligible to enter the study will receive 3 monthly intravitreal (IVT) ranibizumab 0.5mg injections followed thereafter by monthly IVT injections of ranibizumab 0.5mg on a pro re nata/administer as required (PRN) basis. There will be 3 periods in this study: Screening period from Day -70 to Day 0, Monthly Treatment period from Baseline (Day 1) to Day 60, and PRN Treatment period from Day 61 to Day 180.

All assessments will be performed according to the assessment schedule (see Table 6-1 and Table 6-2 in Section 6 of the protocol).

The purpose of this study is to determine, in patients with nAMD treated with aflibercept and where there is evidence of persistent or increasing disease activity, whether switching treatment to ranibizumab 0.5mg reduces disease activity over a 6 month period as assessed by a variety of measures.

2 Statistical and analytical plans

For all patients only one eye will be considered as the study eye, but efficacy and safety parameters will be recorded for both eyes. Data presentations will distinguish study and fellow eye values.

Summary statistics for continuous variables will include n (the number of non-missing observations), mean, standard deviation, minimum, median, maximum, and, where appropriate, 95% confidence interval (CI).

Summary statistics for categorical variables will include frequencies and percentages, and, where appropriate, 95% CI.

Unless otherwise specified, all statistical tests will be two-sided and use the 0.05 level of significance.

All data will be listed by patient, and where applicable, by eye, for all screened patients.

Baseline will be defined as the last available non-missing value collected prior to the start of treatment in the study eye. The protocol deviation review at the end of the study will identify any patients where the gap between the prior reading and the start of the study is too wide, i.e. > 3 days.

For patients with screening assessments who do not enter the treatment period, data will only be listed. For patients who do not enter the treatment period due to a study eye specific exclusion criterion, descriptive statistics as described above will be provided.

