## **2.2 Secondary objectives**

- To evaluate whether treatment with intravitreal ranibizumab 0.5mg is associated with improvements in various retinal morphology parameters as determined by OCT at various time points over a period of 6 months and evaluated by a Central Reading Centre (CRC), including:
  - The change in subfoveal retinal thickness (SRT), central subfield retinal thickness (CSRT) and central subfield retinal volume (CSRV).
  - The proportion of patients with subretinal fluid (SF), intra-retinal cystoid changes (IRC), pigment epithelial detachments (PEDs), or dry retina.
  - The change in size (height or volume as appropriate) of various anatomical parameters including SF, IRC, and PEDs.
- To evaluate changes from Baseline BCVA at various time points over a period of 6 months including changes in BCVA between 3 and 6 months.
- To evaluate ocular and systemic safety by determining the incidence of ocular and systemic adverse events (AEs).

[figure not shown]

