### **6.4.1 Optical Coherence Tomography**

Optical Coherence Tomography (OCT) images are to be taken using High Definition (HD)/Spectral Domain (SD) optical coherence tomography (OCT) equipment. Patients must be assessed using the same machine throughout the course of the study.

The Investigator will perform OCT at visits indicated in Table 6-1 according to a standardized imaging protocol as specified in the Procedure Manual. The information collected will be used by the Investigator to assess the status of disease activity; i.e., decisions on subject eligibility as well as decisions on PRN treatment are based on his/her own evaluation.

The Investigator will send the digital raw images taken monthly from Screening to Day 180 to the Central Reading Center (CRC) as soon as possible after the Scheduled Study Visit; the images will be transferred electronically using the dedicated SD/HD-OCT software format. No transmission of imaging data on print-outs will be accepted. The captured images will contain quantitative parameters (i.e., the Subfoveal Retinal Thickness (SRT), the Central Subfield Retinal Thickness (CSRT), Central Subfield Retinal Volume (CSRV), PED height, SRF volume, IRC volume, and the subfoveal choroidal thickness), as well as the presence or absence of qualitative parameters (IRC, intraretinal fluid, SRF, hemorrhage, dry retina, or other). The CRC will evaluate the images and the results of the CRC assessments will be transferred to the CRO responsible for data management.

The CSRT represents the average retinal thickness ( $\mu\text{m}$ ) of the circular area within 1 mm diameter around the foveal center. The CSRV represent the total retinal volume ( $\mu\text{m}^3$ ) of the circular area within 1mm around the foveal center. Both CSRT and CSRV are based on the automatically determined values from the dedicated SD/HD-OCT software. Before accepting the values provided by the dedicated SD/HD-OCT software, the OCT image acquisition technician must ensure adequate image quality for the assessment of the CSRT. Specifically the technician must exclude any artifacts of the automated segmentation. If artifacts are identified, a manual correction of segmentation lines must be done.

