The SRT represents the retinal thickness ( $\mu\text{m}$ ) measured at the focal center point (center of the anatomical fovea). It is determined on the single most central B-scan with the vitreo-retinal interface as the upper boundary and the lower border of band 4 (presumably RPE/Bruch's membrane) as the lower boundary.

The CRC will provide each site with a manual giving instructions and guidance on how to acquire, export and transfer OCT images. All investigational site personnel performing OCT assessments will be certified by the CRC prior to any study assessments taking place.

Historical OCT images for individual patients will also be evaluated by the CRC. Pseudo-anonymized historical retinal images (including one OCT volume scan acquired no greater than 28 days before the first IVT injection of aflibercept was administered to the study eye) will be collected and electronically transferred to the CRC. In addition, pseudo-anonymized historical retinal OCT images acquired after a minimum of 2 aflibercept injections indicating either no change or worsening disease activity (primary treatment failure subgroup) or an improvement in retinal morphology as defined by a reduction of  $\geq 50\mu\text{m}$  in CSRT (suboptimal treatment response subgroup) will also be collected and transferred to the CRC. The data (i.e., copies of OCT images with relevant written Investigator interpretation) supporting these requirements should be recorded within the source documentation.

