2.2.1.1 Variables

The primary variable will be the difference from baseline to Day 90 in CSRT.

[figure not shown]

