2.2.2 Secondary objectives

2.2.2.1 Variables

Secondary variables are:

From OCT

- Change from baseline to visits up to Day 180 in
 - Subfoveal Retinal Thickness (SRT) (*GRADE*: SUBFOVTK),
 - Central Subfield Retinal Thickness (CSRT) (*GRADE*: CSTTHK),
 - Central Subfield Retinal Volume (CSRV) (*GRADE*: CSRVVOL).
- Presence or absence of qualitative OCT parameters:
 - Intraretinal fluid (*GRADE*: RETFL),
 - Intraretinal fluid of cystoid origin (*GRADE*: RETIRC)
 - Subretinal fluid (SF) (*GRADE*: RETFLSF)
 - Intraretinal/subretinal fluid within the central subfield (diameter 1000 microns) (*GRADE*: RETSF)
 - Pigment epithelial detachments (PEDs) (*GRADE*: PEDDET),

- Dry retina. Dry retina is defined as eye without intraretinal fluid (RETFL from derived.grade) AND eye without subretinal fluid (RETFLSF from derived.grade) AND eye without intraretinal cysts (RETIRC from derived.grade)
- Change from baseline to visits up to Day 180 in PED height (*GRADE*: PEDHEIGHT) and diameter (*GRADE*: PEDDIAM) and IRC height (*GRADE*: IRCHEIGHT).
- Frequency of qualitative change OCT parameters:
 - Change from previous visit, each visit up to Day 180 in intraretinal fluid (*GRADE*: INTRAFL)
 - Change from previous visit, each visit up to Day 180 in subretinal fluid (SF) (*GRADE*: SUBRETFL)
 - Change from previous visit, each visit up to Day 180 in intraretinal/subretinal fluid within the central subfield (*GRADE*: SUBCENT)
 - Change from previous visit, each visit up to Day 180 in the pigment epithelium detachment (PED). (*GRADE*: CHAGPED)

or **From visual acuity (for study eye and fellow eye)**

- Change in BCVA from baseline to visits up to Day 180.
- Change in BCVA from Day 90 to Day 180.
- Proportions of patients with change from baseline in ETDRS letters for the following categories ≤ -15 , > -15 to < 0 , ≤ 0 to < 5 , ≥ 5 to < 10 , ≥ 10 to < 15 and ≥ 15 ETDRS letters from baseline at visits up to Day 180.

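### The SAP assesses subretinal-fluid volume by CSRT and SRT, central thickness measures that cannot isolate subretinal fluid

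*SAP*

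**What the plan says.** Protocol 2.2 makes SF size part of a secondary objective: "The change in size (height or volume as appropriate) of various anatomical parameters including SF, IRC, and PEDs". Protocol 9.5.1 turns this into a variable, "Mean change from baseline to visits up to Day 180 in PED height, SF volume, and IRC volume", listed separately from the changes in SRT, CSRT and CSRV.

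The opening section of the SAP, in its list of changes from the planned analysis, withdraws the volume measurement. On SF and intraretinal-cyst (IRC) volume it says: "Due to technical limitations, there is no robust way in the reading center to assess these two parameters". It then gives a replacement for each. IRC volume is to be judged from maximum IRC height. For SF, "CSRT thickness and subfoveal retinal thickness will be used to assess SF volume".

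Two definitions in Protocol 6.4.1 matter here. For CSRT, "The CSRT represents the average retinal thickness" over the central disc of 1 mm diameter, taken from the OCT software. SRT is a distance at a single point, "with the vitreo-retinal interface as the upper boundary and the lower border of band 4 (presumably RPE/Bruch's membrane) as the lower boundary". CSRT also carries the primary analysis (SAP 2.2.1.1): "The primary variable will be the difference from baseline to Day 90 in CSRT".

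SAP 2.2.2.1 lists CSRT and SRT under their own names and has no SF-volume or SF-height variable. It keeps two grades specific to SF: presence at each visit (RETFLSF) and qualitative change since the previous visit (SUBRETFL).

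**The concern.** The SAP's rule treats a thickness as a reading on one fluid compartment. A change in central thickness combines whatever happens to retinal tissue, intraretinal fluid and, where the boundaries include it, subretinal fluid. If the rule is followed, a thinner centre may be written up as less SF when SF did not change.

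It also counts one measurement under two objectives. The protocol listed SF volume as something distinct from CSRT and SRT. Once SF volume is assessed by those two variables, the SF-size objective receives no evidence beyond what the primary analysis and the existing thickness variables already give.

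The population adds to the problem. The activity criteria in Protocol 4.1 (inclusion criteria 4 and 5) can be met by intraretinal or sub-RPE fluid or by a PED, so an eye can enter with no SF. SAP 2.2.2.2 analyses secondary variables in the whole FAS, so thinning in such eyes would feed into a statement about SF volume.

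What is at stake is the conclusion the report may draw on SF size, both at the end and in the interim analysis of the first 50 patients. SAP 2.5 includes the secondary variables in that analysis and sends its results for publication.

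**Working it through.** No figure in the plan is in dispute. The check compares definitions and adds a small illustration.

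**1. What the substitutes contain.** Within the measured region, write the change in thickness as

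ΔT = Δtissue + Δintraretinal fluid + ΔSF.

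This is one observed quantity and three unknown components, so ΔT fixes neither the size nor the sign of ΔSF. For SRT the boundaries are stated, and subfoveal SF lies between them. For CSRT, Protocol 6.4.1 gives the area but not the segmentation boundaries, so its content is inferred from the description as average retinal thickness. If CSRT's boundaries exclude SF, the ΔSF term drops out and CSRT says even less about it.

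**2. Illustration.** The thickness changes are assumed; the documents give none for this purpose. The disc area follows from the 1 mm diameter: π × (0.5 mm)² = 0.7854 mm².

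| Assumed CSRT change | Volume change in the disc |
|---|---|
| 10 µm | 0.7854 × 0.010 = 0.0079 mm³ |
| 30 µm | 0.7854 × 0.030 = 0.0236 mm³ |
| 50 µm | 0.7854 × 0.050 = 0.0393 mm³ |

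These are changes in total volume. The next table shows how little a CSRT change says about SF, taking CSRT to include SF and tissue to be unchanged. Entries are mean µm over the disc.

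| Case | SF | Intraretinal fluid | CSRT change | True central SF volume change |
|---|---|---|---|---|
| A | 0 | −30 | −30 | 0 |
| B | −30 | 0 | −30 | −0.0236 mm³ |
| C | −30 | +30 | 0 | −0.0236 mm³ |

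A and B have the same CSRT change and different SF changes. B and C have the same SF change and different CSRT changes. If CSRT excludes SF, case B gives 0 and case C gives +30, which is worse. SF lost or gained outside the central 1 mm changes neither CSRT nor SRT.

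**3. How the SAP treats the neighbouring compartments.**

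| Compartment | Size measure in the SAP | Specific to the compartment? |
|---|---|---|
| IRC | maximum height | yes |
| PED | height and diameter | yes |
| SF | CSRT and SRT | no |

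Protocol 2.2 allows height or volume, so SF height would have met the objective. It does not appear in SAP 2.2.2.1.

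**4. What SF-specific data remain.** RETFLSF is tabulated at baseline (SAP 2.1.4) and at each visit (SAP 2.2.2.1), so a comparison with baseline is possible. SUBRETFL refers to the previous visit, so it cannot by itself give change from baseline.

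**The case against.** The strongest reply is that the sentence does little. The SAP's variable list has no SF-volume output. CSRT and SRT are reported under their own names, as the protocol already planned, and SF presence and SF change are tabulated by visit. The change is disclosed with a reason, the secondary analyses are descriptive, and Protocol 3.2 calls the study exploratory. Most of this stands, and it limits the stakes. It does not remove the problem. The sentence is a current rule on how the thickness results are to be used, and it carries no caution about reading them as SF.

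Three stronger readings are tempting, and the documents do not support them.

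- A reader might infer that CSRT and SRT say nothing about SF. SRT's stated boundaries take in subfoveal SF, so the accurate description is non-specific, not uninformative.
- A reader might infer that every fall in CSRT will be reported as a fall in SF. No table, test or claim of that kind is specified; the rule permits such a reading but does not produce it automatically.
- A reader might take the 30 to 50 µm illustration as an estimate of the error. It is a unit conversion of assumed changes and does not show how far CSRT would mislead in this trial.

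Two entries in the SAP's change list are redacted. Nothing is inferred from them.

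**Conclusion.** The substitution is wrong as written. By the protocol's own definitions, CSRT and SRT cannot isolate SF, and they give the SF-size objective no evidence beyond the primary variable and the existing thickness variables. For SRT this rests on stated boundaries. For CSRT it rests on the description as average retinal thickness, and it holds whether or not the software's boundaries include SF.

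The effect is limited to what may be concluded about SF size in a descriptive secondary analysis. The visible text specifies no hypothesis test on SF volume, so type I error, sample size and the primary result are untouched. SF is not left unassessed either, because presence and qualitative change remain; what is lost is a valid quantitative measure of its size.

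**What to change.** Change the SAP wording as follows, before any results on SF are published, the interim results included.

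1. Delete the statement that CSRT and SRT assess SF volume, and state that SF volume is not evaluable. Report CSRT and SRT only as thickness endpoints.
2. Answer the SF objective with RETFLSF by visit in the whole FAS, with a baseline-to-visit shift table that shows resolved, persistent, newly developed and absent SF. Include a missing category, since SAP 2.2.2.2 does not replace missing secondary data. Do not restrict the analysis to eyes with SF at baseline: such eyes can only stay the same or improve, and new SF would be hidden.
3. Present SUBRETFL as change from the previous visit only.
4. If the reading center can already grade SF height on the existing scans, use it as the size measure, as Protocol 2.2 allows.

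The cost is SAP text and one additional table, plus regrading of existing scans if SF height is adopted. The downside is that the quantitative SF-volume endpoint is given up, though the SAP already says it cannot be measured robustly.
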